9.3.2 Outcomes

We will examine the treatment patterns of patients with MHT.

- 1) Prevalence of menopausal symptoms and use of MHT among women aged 40 – 59 years.
 - The annual prevalence of menopausal symptoms will be calculated as the number of women diagnosed with menopausal symptoms divided by the mid-year population of women aged 40 – 59 years.
 - The annual prevalence of menopausal symptoms with MHT will be calculated as the number of women diagnosed with menopausal symptoms and prescribed with MHT divided by the mid-year population of women aged 40 – 59 years.
- 2) Prevalence of each menopausal symptom among patients with MHT.
 - Menopausal symptoms will be classified into 4 categories: vasomotor symptoms, bone and joint symptoms, genitourinary symptoms, and psychosomatic symptoms. (Table 3)
 - The prevalence of each menopausal symptom among patients with MHT will be calculated as the number of patients diagnosed with each menopausal symptom divided by the number of patients prescribed for MHT.

Table 3. Menopausal symptoms

Menopausal symptoms	KCD-8 code
Vasomotor symptoms	N95.1 (Menopausal and female climacteric states) N95.3 (States associated with artificial menopause) N95.8 (Other specified menopausal and perimenopausal disorders) N95.9 (Menopausal and perimenopausal disorder, unspecified) R23.2 (Flushing) [§]
Bone and joint symptoms	M80.0 (Osteoporosis with pathological fracture) M81.0 (Postmenopausal osteoporosis) M81.99 (Osteoporosis, unspecified, site unspecified; Osteopenia)

	M85.99 (Disorder of bone density and structure, unspecified, site unspecified; Osteopenia, mild; Osteopenia, moderate; Osteopenia, severe)
Genitourinary symptoms	N94.1 (Dyspareunia) N95.0 (Postmenopausal bleeding) N95.2 (Postmenopausal atrophic vaginitis) F52.6 (Nonorganic dyspareunia)§
Psychosomatic symptoms	F32 (Depressive episode)§ F33 (Recurrent depressive disorder)§ F51 (Nonorganic sleep disorders)§ G47 (Sleep disorders)§

§R23.2, F32, F33, F51, F52.6, G47 are considered as diagnosis codes for menopausal symptoms only when they are obtained by obstetrics and gynecology specialists. (DGSBJT_CD:10)

- 3) Secular trend in the prevalence of MHT by treatment class, age group, menopausal symptoms, and the type of administration
 - We will examine annual and quarterly time-series trends in the prevalence of MHT between January 1, 2012, and December 31, 2020.
 - First, we will examine trends by 3 classes of MHT: ET (estrogen therapy), EPT (estrogen-progestin therapy) and tibolone. The time-series trend will be presented as the proportion of each class of MHT quarterly, calculated as the number of patients receiving each class of MHT divided by the total number of patients prescribed with MHT.
 - Second, we will examine trends by age group: all, 40-44, 45-49, 50-54, and 55-59. The time-series trend will be presented as the proportion of MHT use by each age group, calculated as the number of patients in each age group divided by the total number of patients prescribed with MHT.
 - Third, we will examine trends by menopausal symptoms: vasomotor symptoms, bone and joint symptoms, genitourinary symptoms, and psychosomatic symptoms. The time-series trend will be presented as the proportion of MHT use by each menopausal symptom, calculated as the

number of patients with each menopausal symptom divided by the total number of patients prescribed with MHT.

- Fourth, we will examine trends by the type of administration: systemic HT (oral), systemic HT (transdermal) and local HT (transvaginal). The type of administration of MHT will be classified as follows (Table 4). The time-series trend will be presented as the proportion of MHT use by each type of administration, calculated as the number of patients with MHT by each type of administration divided by the total number of patients prescribed with MHT.

Table 4. Type of administrations

Type of administrations	Ingredient code
Systemic HT (oral)	All ingredient codes except those for systemic HT (transdermal) and local HT (transvaginal)
Systemic HT (transdermal)	154902CCM 154904CPC 154905CPC 154906CPC 154907CSI 154908CCM 154908COM 154930CCM 154931CCM 154932CCM 154601CPC 154602CPC 154603CPC 154604CPC 154605CPC 154606CPC 335900CPC 336000CPC

Local HT (transvaginal)	155303CCM 155402CCM 155430CCM 155201CCM 155202CSP 507700CTB 336200CTB 155502CCM 219001CCS 219001CCM 219030CCM 336100CTB
-------------------------	--

4) Treatment regimens change of MHT across time

- We will depict treatment switch and discontinuation patterns across time by measuring the number of different treatments, including ET, EPT and tibolone, at time points of 3, 6, 9, and 12 months from the index date. Switching and discontinuation of MHT across time will be presented with a Sankey diagram.

5) Time to switch and discontinuation of MHT

- Over time since the index date (initiation of MHT), Kaplan-Meier survival curves will be generated to calculate the time to non-persistence events including switch and discontinuation. Discontinuation will be defined as no subsequent prescriptions within 2 months of last prescription date.
- Switching MHT for any other treatment classes. (i.e. Switch will be defined as when a patient initiating a ET is prescribed a tibolone or EPT)

6) Treatment persistence and adherence

- Treatment persistence is calculated by the average length of treatment of the drugs prescribed at the index date. Persistence rate at 3-, 6-, 9-, and 12-month will also be calculated.

- Treatment adherence will be evaluated using medication possession ratio (MPR), calculated as the total number of days of medication supply divided by the number of days in the follow-up period.

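### Table 3 counts 'other specified' and 'unspecified' menopausal codes as vasomotor symptoms, with no stated reason and no analysis showing the result without them

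*Combined protocol and SAP*

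**What the plan says.** Section 9.3.2 sorts menopausal symptoms into four groups by diagnosis code (Table 3). The vasomotor group holds five codes: "N95.1 (Menopausal and female climacteric states", "N95.3 (States associated with artificial menopause", "N95.8 (Other specified menopausal and perimenopausal disorders", "N95.9 (Menopausal and perimenopausal disorder, unspecified" and "R23.2 (Flushing".

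A footnote restricts R23.2 and the depression, sleep and nonorganic dyspareunia codes: they "are considered as diagnosis codes for menopausal symptoms only when they are obtained by obstetrics and gynecology specialists". The N95 codes carry no such restriction.

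The groups are used twice. Outcome 2 is "calculated as the number of patients diagnosed with each menopausal symptom divided by the number of patients prescribed for MHT". Outcome 3 repeats the grouping over time: "Third, we will examine trends by menopausal symptoms: vasomotor symptoms, bone and joint symptoms, genitourinary symptoms, and psychosomatic symptoms". Sections 9.2 and 9.7 set the symptom window at 90 days from cohort entry. Table 3 has no residual or unspecified group.

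The two sensitivity analyses in section 9.3.4 concern a 4-month discontinuation gap and patients with 2 years of follow-up. Section 9.9 acknowledges in general terms that claims diagnoses can differ from true disease. Section 9.4 gives an overall positive predictive value of 82% for diagnoses in the Korean data, not a value for any N95 subcode or for vasomotor symptoms.

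**The concern.** By the protocol's own labels, N95.9 says nothing about which symptom was present, and N95.8 says only that it was something other than the named conditions. Counting both as vasomotor adds information that the claim does not hold. The rule is also uneven: an unspecified menopausal diagnosis from any specialty counts as vasomotor, while recorded flushing counts only from obstetrics and gynecology.

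Prevalence of MHT by menopausal symptom is part of objective 1. Section 7 notes that guidelines recommend MHT for vasomotor symptoms and for preventing osteoporosis, so the vasomotor share is likely to be read as a measure of guideline-concordant use. If part of that share consists of unspecified diagnoses, the reader should be able to see how much. Likewise, a change between 2012 and 2020 in how often N95.8 or N95.9 is used could appear as a change in vasomotor symptoms.

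**Working it through.** **1. Which entry codes lead to which group.** Comparing Table 1 (nine entry codes) with Table 3:

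| Table 3 group | Entry codes from Table 1 | Count |
|---|---|---|
| Vasomotor | N95.1, N95.3, N95.8, N95.9 | 4 |
| Bone and joint | M80.0, M81.0, M81.99, M85.99 | 4 |
| Genitourinary | N95.2 | 1 |
| Psychosomatic | none | 0 |

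The counts sum to 4 + 4 + 1 + 0 = 9. A woman who enters on any N95 code other than N95.2 is counted as vasomotor, provided the entry-day claim falls inside the 90-day window. Of the five vasomotor codes, only R23.2 has a label that names a vasomotor symptom. These are counts of codes and say nothing about shares of patients.

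**2. What the two codes add.** Let f be the proportion of MHT patients whose only vasomotor code is N95.8 or N95.9. Then

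share under Table 3 − share without N95.8 and N95.9 = f, with f ≥ 0.

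This is exact and needs no assumption about the women's true symptoms.

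**3. Can f be found in the documents?** No. The protocol states no vasomotor share to reproduce, and its only N95 counts are in Table 7. Its age rows sum to the printed yearly totals, and these sum to the stated figure: 591,775 + 574,602 + 543,226 + 526,981 + 521,527 + 518,129 + 507,824 + 509,683 = 4,293,747. The table is correct, but it is not split below N95 and does not count MHT patients.

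**4. Comparison with the true share.** Let q be the proportion of the f group who truly have vasomotor symptoms, and m the share of MHT patients who have vasomotor symptoms but no vasomotor code. Then

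share under Table 3 − true share = f(1 − q) + other false positives − m.

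None of these terms is in the documents. For assumed values, f(1 − q) in percentage points is:

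| f | q = 0 | q = 0.5 | q = 1 |
|---|---|---|---|
| 5% | 5.0 | 2.5 | 0 |
| 10% | 10 | 5 | 0 |
| 20% | 20 | 10 | 0 |
| 30% | 30 | 15 | 0 |

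Missed cases can reverse the sign. Ignoring other false positives, f = 10% and q = 0.5 give 5 − 0 = +5 points for m = 0, 5 − 5 = 0 for m = 5%, and 5 − 10 = −5 for m = 10%.

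**5. Trend.** Suppose coding shifts by x points of MHT patients. If women move from N95.2 alone to N95.9 alone, the Table 3 vasomotor share rises by x and the share without N95.8 and N95.9 is unchanged. If they move from N95.1 alone to N95.9 alone, the Table 3 share is unchanged and the narrower share falls by x. Each definition can show a false trend that the other does not.

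**The case against.** The strongest reply is that a longer code list always gives a share at least as large as a shorter one, and that this alone is not bias. A reader might infer that Table 3 overstates the vasomotor share by construction. The documents do not support that. Some women coded N95.8 or N95.9 may well have vasomotor symptoms, and the specialty restriction on R23.2 works in the other direction by missing some recorded flushing. Step 4 shows that the net sign is open. This part of the reply stands.

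A second reply is that no narrower list is clearly better. A reader might infer that vasomotor should simply mean N95.1 plus R23.2. But the label of N95.1 is a general menopausal one and names no vasomotor symptom either, and step 5 shows that a narrow list as the only definition could produce a false trend of its own. This also stands. It argues for showing both versions, not for replacing one unvalidated definition with another.

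Third, the consequences are limited. The study is descriptive, the code list is printed in full, and switching, discontinuation, persistence and adherence do not use Table 3. The groups are not stated to be mutually exclusive, so the other symptom shares need not change. That limits the weight of the point but does not remove it, because the symptom results are stated outcomes.

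What does not stand is that claims data allow nothing better. They cannot show whether a woman coded N95.9 had hot flushes, but N95.9 is a distinct code and can be reported as such.

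**Conclusion.** The point holds in a limited form. N95.8 and N95.9 are counted as vasomotor although their labels name no vasomotor symptom. No reason is given, and no planned analysis would show the effect. The certain consequence is that the reported share exceeds the share without these codes by exactly f. The size of f is unknown: 5 to 30 points corresponds to an assumed range, not to any figure in the protocol. The direction and size of any bias against the true share cannot be determined from the documents, so a claim that the share is overstated should not be made. N95.1 and N95.3 raise the same question by label, which means that removing N95.8 and N95.9 gives a narrower group but not a purely vasomotor one. This should be corrected before analysis. It affects the symptom breakdown in outcomes 2 and 3 and leaves the treatment-pattern results untouched.

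**What to change.** - In outcome 2 and in the symptom trend of outcome 3, report patients whose only vasomotor code is N95.8 or N95.9 (either or both, without N95.1, N95.3 or R23.2) as a separate row, 'other/unspecified menopausal disorder'.
- Show the vasomotor share and its trend both with and without that row.
- Show N95.3 separately in the same way. State where a woman is counted who has N95.3 together with N95.8 or N95.9 but neither N95.1 nor R23.2, since she fits neither single-code row.
- In section 9.9, state that N95.1 is also a general menopausal code, so that the group is read as vasomotor or general menopausal codes. Give the reason for the mapping if there is one.

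This uses codes already in the requested data. For N95.8 and N95.9 the cost is one more output row and a second version of the vasomotor share and trend; N95.3 adds the same again. The drawback is a possibly lower vasomotor percentage in the narrower version.

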7. RATIONALE AND BACKGROUND

Women at menopause may experience various changes due to ovarian failure and sex hormone deficiency¹. Globally, more than half of women aged 40-64 years experience menopausal symptoms such as hot flushes, night sweating, palpitation, sexual dysfunction, depression, insomnia and osteoporosis². These symptoms can disrupt various aspects of a person's life such as their ability to sleep, concentrate, maintain a good mood, feel energetic, carry out work, and engage in leisure or social activities³. Furthermore, the burden of medical treatment for menopausal symptoms is substantial and keeps increasing, highlighting the need for effective solutions to improve the quality of life for these population⁴.

Treatment guidelines recommend MHT for vasomotor symptoms and prevention of osteoporosis in women under 60 years of age or within 10 years of menopause and without contraindications⁵. However, since the Women's Health Initiative report and the Million Women Study were published, the use of MHT has declined rapidly^{6,7}. Also, many studies have reported a potential link between MHT and increased risk of cardiovascular disease, breast cancer, and endometrial hyperplasia⁸⁻¹⁰. Therefore, many menopausal individuals also seek treatment alternatives to MHT, including selective serotonin reuptake inhibitors, serotonin-norepinephrine reuptake inhibitors, gabapentin, and clonidine¹¹, although some of them have limited effectiveness and are also associated with specific adverse effects¹².

Recently, in light of the position statement on MHT, several menopause societies concur on the necessity of individualized MHT^{13,14}. Given that there is limited evidence on the latest MHT usage pattern using the most recent data in South Korea, we aim to estimate the prevalence of MHT among menopausal women and understand treatment patterns, adherence, and persistence among patients with menopausal hormone therapy in South Korea using the nationwide claims database from 2011 to 2020.

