8. RESEARCH QUESTION AND OBJECTIVES

- Research question: What are the real-world usage patterns of menopausal hormone therapy in South Korea?
- Objectives

1. To estimate the prevalence of MHT by treatment class, age group, menopausal symptoms, and the type of administration
2. To describe the baseline characteristics of patients prescribed with or without MHT
3. To examine treatment patterns, adherence, and persistence among patients with MHT

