9.7. Data analysis

We will investigate the baseline characteristics of patients with MHT. Baseline characteristics such as age, insurance type and income levels, and medical institution type will be assessed on cohort entry date. Baseline characteristics such as CCI, no. of outpatient visits/hospitalization, comorbidities and concomitant medications will be assessed on during a 1-year period before cohort entry date. Type of administration will be assessed on index date. The results will be presented in frequency (proportion) for categorical variables and mean (SD) or median (IQR) for continuous variables.

All outcome variables will be summarized descriptively through the tabular or graphical form of means, medians, ranges, and standard deviations of continuous variables and frequency distributions of categorical variables.

Annual time-series prevalence of menopausal symptoms and use of MHT will separately be calculated among total women aged 40-59.

The prevalence of each menopausal symptom among patients with MHT will be calculated as the number of patients diagnosed with each menopausal symptom divided by the number of patients diagnosed and prescribed for MHT. Menopausal symptoms, assessed within 90 days after the cohort entry date, will be classified into 4 categories: vasomotor symptoms, bone and joint symptoms, genitourinary symptoms, and psychosomatic symptoms.

We will examine annual and quarter time-series trends in the prevalence of use for MHT by treatment class, age group, menopausal symptoms, and the type of administration between 2012 and 2020.

We will examine annual and quarterly time-series trends in the prevalence of MHT use by 3 types of MHT: ET (estrogen therapy), EPT (estrogen-progestin therapy), and tibolone. The time-series trend will be presented as the proportion of each type of MHT quarterly, calculated as the number of patients receiving each type of MHT divided by the total number of patients prescribed with MHT.

We will examine annual time-series trends in the prevalence of MHT use by age group: all ages, 40-44, 45-49, 50-54, and 55-59. The time-series trend will be presented as the proportion of MHT use by each age group, calculated as the number of patients in each age group divided by the total number of patients prescribed with MHT.

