We will examine annual time-series trends in the prevalence of use for MHT by menopausal symptoms: vasomotor symptoms, bone and joint symptoms, genitourinary symptoms, and psychosomatic symptoms. The time-series trend will be presented as the proportion of MHT use by each menopausal symptom, calculated as the number of patients with each menopausal symptom divided by the total number of patients prescribed with MHT.

We will examine annual time-series trends in the prevalence of use for MHT by the type of administration: systemic HT (oral), systemic HT (transdermal) and local HT (transvaginal). The time-series trend will be presented as the proportion of MHT use by each type of administration, calculated as the number of patients with MHT by each type of administration divided by the total number of patients prescribed with MHT.

Switching and discontinuation of MHT for any other MTH type will be shown by using Kaplan-Meier curve. Discontinuation will be defined as no subsequent prescriptions within 2 months of last prescription date. We will conduct a sensitivity analysis where discontinuation of MHT is defined as a 4-month period without any MHT.

Treatment persistence is calculated by the average length of treatment of the drugs that were prescribed at the index date. Treatment adherence will be shown by calculating MPR (medication possession ratio), calculated as a total number of days of supply of medication divided by the number of days of the follow-up period.

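### Objective 1 asks for MHT prevalence by group, but the trend formulas give the distribution of MHT users: symptom and age lack the denominator they need, class and route are only mislabelled

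*Combined protocol and SAP*

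**What the plan says.** Section 8 gives the first objective as "To estimate the prevalence of MHT by treatment class, age group, menopausal symptoms, and the type of administration". Section 7 names the population: "we aim to estimate the prevalence of MHT among menopausal women and understand treatment patterns, adherence, and persistence". Item 3 of section 9.3.2 is headed as a secular trend in the prevalence of MHT along the same four dimensions.

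The formulas, in 9.3.2 item 3 and again in 9.7, all share one denominator. For age the ratio is "calculated as the number of patients in each age group divided by the total number of patients prescribed with MHT", with 'all' listed as one of the levels. For symptom it is "calculated as the number of patients with each menopausal symptom divided by the total number of patients prescribed with MHT". Class and route are built the same way. Each is described as a proportion, and numerator and denominator are stated openly.

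Two neighbouring outcomes matter here. Item 1 of 9.3.2 gives two annual figures on the mid-year population of women aged 40-59, pooled over age: women with a menopausal diagnosis, and women with a diagnosis and MHT. Item 2, on symptoms among MHT patients, is "calculated as the number of patients diagnosed with each menopausal symptom divided by the number of patients prescribed for MHT".

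On symptom timing, 9.7 says: "Menopausal symptoms, assessed within 90 days after the cohort entry date, will be classified into 4 categories". The Table 3 footnote adds that six of its codes "are considered as diagnosis codes for menopausal symptoms only when they are obtained by obstetrics and gynecology specialists".

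The population is described in more than one way. The Abstract (Data analysis) promises yearly prevalence by group within the final study cohort, without a formula. Section 9.2 defines that cohort as women who started MHT. Section 9.2.1 requires only age and a diagnosis. Objective 2 is "To describe the baseline characteristics of patients prescribed with or without MHT".

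**The concern.** Prevalence of MHT in a group is the treated women in that group divided by all women in that group. In the item 3 formulas no untreated woman enters any denominator, so the result is the make-up of the treated population.

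This is the first-listed objective of a descriptive study, so the denominator is the estimand. A changing share labelled as prevalence can be read as changing use when the treated fraction is constant, and a flat share can hide a fall within a band. For symptom, the trend formula repeats the form of item 2: one ratio serves as symptom frequency among users and, by its label, as MHT use by symptom.

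**Working it through.** **1. Formulas side by side.**

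| Dimension | Objective 1 needs | 9.3.2 item 3 and 9.7 give | Gap |
|---|---|---|---|
| Symptom | P(MHT given symptom) | P(symptom given MHT), the form of item 2 | No planned output states MHT use among women with a symptom |
| Age | P(MHT given band) | P(band given MHT) | No band denominator; 'all' is 100% by construction |
| Class, route | Users of class or route / women | Users of class or route / all users | Valid mix measure; label wrong |

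**2. The plan's own figure.** Table 7 (section 9.5) counts women with an N95 primary diagnosis. The bands add to the column totals: 2012, 23,651 + 117,078 + 264,843 + 186,203 = 591,775; 2019, 13,477 + 84,398 + 203,940 + 207,868 = 509,683. The eight yearly totals sum to the stated 4,293,747.

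Table 7 contains no MHT users and omits the M80, M81 and M85 entry codes. In steps 3 and 4 it stands in for diagnosed women, and the treated fractions are assumptions.

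**3. Use flat, planned figure moves.** Let the treated fraction be r in every band and year. The planned figure is r × band / (r × total) = band / total, whatever r is.

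| Band | 2012 | 2019 |
|---|---|---|
| 40-44 | 4.0% | 2.6% |
| 45-49 | 19.8% | 16.6% |
| 50-54 | 44.8% | 40.0% |
| 55-59 | 31.5% | 40.8% |

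The 55-59 figure rises 9.3 points while use among diagnosed women is flat in every band. If the constant treated fraction at 55-59 is half that of the other bands, the figure goes from 18.7% to 25.6%; if double, from 47.9% to 57.9%. The rise is then about 7 to 10 points.

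**4. Use falls, planned figure is flat.** The factor on the 2019 treated fraction at 55-59 that keeps its share at the 2012 value is (186,203 / 405,572) × (301,815 / 207,868) = 0.667, where 405,572 and 301,815 are the totals of the other three bands. With that factor, 55-59 shows 31.5% in both years and 50-54 goes from 44.8% to 46.3% (203,940 / 440,382). Use among diagnosed women aged 55-59 has gone from 20.0% to 13.3% (10.0% to 6.7%, or 40.0% to 26.7%, from other assumed starting levels).

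**5. What item 1 would show.** Its second figure divided by its first gives MHT use among diagnosed women, pooled over ages. If use halves in every band, the age shares do not move, but item 1 falls by half. In step 4, starting from 20.0%, the pooled figure falls to 20.0% × 440,382 / 509,683 = 17.3%. The change is visible, but nothing planned places it in the 55-59 band.

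**6. Symptom.** No size can be computed, because the number of women with each category is not given. A hypothetical shows the point: if 600 of 1,000 users have a symptom, the planned figure is 60%; use among women with that symptom is 60%, 30% or 10% if 1,000, 2,000 or 6,000 women have it.

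**7. Class and route.** Share × overall prevalence gives prevalence if the numerators match. A 40% share with an assumed overall 4% gives 1.6%. This works by year only, because item 1 is annual while the class series is also quarterly.

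**8. Codes.** Table 3 lists 17 codes (5 vasomotor, 4 bone and joint, 4 genitourinary, 4 psychosomatic). Eight are not entry codes in Table 1: R23.2, N94.1, N95.0, F52.6, F32, F33, F51 and G47. All four psychosomatic codes are among them.

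**The case against.** The best defence is that nothing is hidden. Every formula is stated and called a proportion, and openly defined shares bias no estimate in a descriptive study. Overall use is covered by item 1, which would reveal a uniform rise or fall. The claims data hold the missing denominators. There is also text pointing to untreated women: Objective 2, the diagnosis-only criteria in 9.2.1, and an Abstract sentence on baseline characteristics of patients with menopausal symptoms. With age bands set at cohort entry (9.3.3), that could yield a pooled treated fraction by band. The study flowchart cannot be checked in the text supplied.

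Much of this stands, and it rules out three stronger readings that a reader might infer. First, MHT use by symptom is not lost; it is absent from the planned outputs. Second, the plan is not blind to a general change in use. Third, the class and route shares are not invalid.

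What remains is that no formula uses a group denominator. The hints do not supply one: 9.3.3 and 9.7 describe baseline characteristics of patients with MHT, and 9.2 makes every cohort member an MHT starter. Whether untreated women are counted is open, and even the favourable reading gives no annual trend by band or symptom.

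A caution also applies to the remedy. Use among diagnosed women is not immune to coding practice. Hypothetically, 200 treated of 1,000 diagnosed is 20%; add 500 newly coded, untreated women and it is 13.3%, with nobody's treatment changed.

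**Conclusion.** The point holds, and should be fixed before analysis. As written, 9.3.2 item 3 and 9.7 do not answer Objective 1 for symptom and age; for class and route the correction is one of wording, plus an annual figure on the item 1 denominator.

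A reader might take the 9.3-point rise or the one-third fall as the expected error. The documents do not support that. Both rest on N95 counts and assumed treated fractions, the fall was solved for so as to hold the share constant, and flat use in the first case means flat among diagnosed women. The result on the band population is unknown, since no band populations are given. The figures show that the planned measure can move without a change in use and stay still despite one. The mismatch of denominators follows from the text alone and needs none of these assumptions.

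**What to change.** In 9.3.2 item 3 and 9.7:

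1. **Age.** Add women in the band with MHT in the year, divided by women in that band diagnosed with menopausal symptoms in that year, with age taken in that year for both. Also divide by the KOSIS mid-year female population of the band, if available; section 9.4 does not mention five-year bands, so this must be confirmed. State that the diagnosed-women ratio can move if coding practice changes.
2. **Symptom.** Add women with the category and MHT in the period, divided by all women with that category in the period. Apply the Table 3 specialist rule to numerator and denominator alike. Require a Table 1 code in both, so that the item 1 counts need only be split. Without that requirement, women who have only the eight non-entry codes must be counted additionally.
3. **Class and route.** Keep the shares and add annual users divided by the item 1 denominator, with the same numerator population as item 1.
4. **Labels.** Call all the planned ratios 'distribution of MHT users'.
5. **Population.** Reconcile the Abstract, 9.2, 9.2.1 and Objective 2 so that the prevalence denominator includes diagnosed women without MHT.

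The cost is protocol wording and a few extra table columns, with slightly more programming if no Table 1 code is required for the symptom categories.
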